19. Collect cytokines at predose (within 30 minutes prior to SOI) and EOI (± 5 min) (even when infusion is interrupted or halted) to assess allergic reaction)
20. All ADA samples will be collected prior to each infusion
21. PK samples to be taken (in all subjects) for both GSK2857916 and cys-mcMMAF measurement: C1D1 at pre-dose (within 30 minutes prior to SOI), 0.5 h after the start of the infusion (SOI) (± 5 min), at the end of infusion (EOI) just before EOI, 1 h after EOI, 3 h after EOI (± 5 min), 8 h after EOI (± 15 min), 24h after EOI (± 1 h) (Day 2); C1D8 1 sample; C1D15 1 sample; C2D1, at pre-dose (within 30 minutes prior to SOI) and at the EOI (just before EOI); C3D1 at pre-dose (within 30 minutes prior to SOI) and at the EOI (just before EOI).
22. Collect 1 PK sample at each subject's final visit.
23. Pre-specified amounts of urine will be collected for PK analysis from the 24 hour urine collection at Screening, C2D1, C4D1, C7D1, C10D1, C13D1, and C16D1. Refer to Section 7.4.2 of the protocol for details.
24. Study drug administration ± 3 day window only
25. Prophylaxis with prednisolone phosphate 1% or dexamethasone 0.1% 1 drop QID x 4 days starting 1 day prior to treatment
26. Record subject's survival status and whether subsequent treatment for disease was given. Subject does not need to come in for visit.

Abbreviations:

ADA = Antibody Drug Antibody; ALP = alkaline phosphatase; BCVA = best corrected visual acuity; BNP = B-type natriuretic peptide; C1D1 = Cycle 1 Day 1, etc.; cfDNA = Circulating free DNA; CK = creatinine kinase; CRP = C-reactive protein; EM = extramedullary; EOI = End of Infusion; FLC = free light chain; PD = Pharmacodynamics; PK = Pharmacokinetics; QID = 4 times a day; SOI = start of infusion; SPEP = serum protein electrophoresis; UPEP = urine protein electrophoresis

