16.9. Appendix 9: Population Pharmacokinetic (PopPK) Analyses

16.9.1. Population Pharmacokinetic (PopPK) Dataset Specification

Any deviations between the dataset specification and the final dataset will be documented in the population pharmacokinetic analysis report.

General Description:

1. The type of variables should be either NUM or DATE/TIME unless specified otherwise
2. The dataset is sorted by ID, RTFDD, ANALYTE, ASCENDING EVID unless specified otherwise
3. The data items (columns) in the analysis-ready data file will be in the same order as described in the table below.
4. Exclude observations with DTYPE=IMPUTE
5. Include PKFL=Y (applicable to all datasets)
6. Same rules are applied for all baseline covariates. Baseline rules are as follows:
 - Use baseline value as defined by Stats in the lab test datasets and fill it on all rows for each subject;
 - If not defined by Stats, set to measurement nearest to, but prior to, time of first dose
 - Only in cases where Day 1 measurement is not available, but screening measurement is, the screening values will be used.
 - Only in cases where both the Day 1 measurement as well as screening measurement are unavailable, set to -99.
7. 3 significant figures for all values except C, STUDY, SUBJID, ID, CTIME, DATE, ANALN, BQL, MDV, MDV2, OCC, CYCLE, CMT, AGE, GENDER, CANCER, RACE, ETHN, CNC, EXTSMP
8. Only subjects with CANCER=0 will be included in this dataset as the data for the lymphoma patients will not be fully cleaned at the time of the database cut in 4Q2018.

CONFIDENTIAL

BMA117159

Column Header	Data Item	Codes	Derivation/Comments	Source data set
C	Line number/exclusion identifier	Row Number STM DRM PFD	Set to line/row number unless one or more of the following conditions are met, then set to code: 
 • STM = If a PK sample was taken but the date and/or time of the sample is missing and cannot be derived • DRM= PK samples for which dosing records are missing • PFD=PK samples with CONC reported as NA/NR/NQ/BQL/missing at pre-dose in CYCLE =1 	derived
STUDYID	Study ID		Unique identifier for a study	adpc
SITEID	Unique identifier for a study site			adsl
USUBJID	Unique subject identifier			adsl
SUBJID	Subject identifier from source data		SUBJID = SUBJID	adsl
ID	NONMEM subject identifier		Sequential subject identifier across studies after data is sorted by SUBJID. For study BMA117196, the ID will start with PPD For study 205678, the ID will start with PPD	derived

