AMT	Amount of GSK2857916 given (in mg)		AMT = ALTDOSE, where PARAMCD=ALTDOSE only on the dosing line. If infusion was stopped early and then restarted, the dosing information will be captured with more than one line. Each line will represent a part of the infusion (for example from start to first interruption and then from restart to end of infusion). AMT will have to be derived separately from restart of infusion until it is stopped. For all other lines use "0"	adex
INFD	Infusion Duration (day)		INFD is the infusion duration and is computed from start and stop time of infusion (in days) (AENDTM-ASTDTM)/60/60/24 This value will only be used on the dosing line. For all other lines use "0" If infusion was stopped early and then restarted, INFD will have to be derived separately from restart of infusion until it is stopped.	adex
INFH	Infusion Duration (h)		INFH is the infusion duration and is computed from start and stop time of infusion (in h) (AENDTM-ASTDTM)/60/60 This value will only be used on the dosing line. For all other lines use "0" If infusion was stopped early and then restarted, INFH will have to be derived separately from restart of infusion until it is stopped.	adex

CONFIDENTIAL

BMA117159

Column Header	Data Item	Codes	Derivation/Comments	Source data set
RATED	Rate of infusion (mg/day)		RATED = AMT/INFD; This value will only be used on the dosing line. For all other lines use "0" If infusion was stopped early and then restarted, RATED will have to be derived separately from restart of infusion until it is stopped.	derived
RATEH	Rate of infusion (mg/h)		RATEH = AMT/INFH This value will only be used on the dosing line. For all other lines use "0" If infusion was stopped early and then restarted, RATEH will have to be derived separately from restart of infusion until it is stopped.	derived
RTFDD	Relative time from start of first infusion on study (day)		$RTFDD = ((ADTM - ASTDTM) / 60 / 60 / 24)$	adpc, adex
RTFDH	Relative time from start of first infusion on study (h)		$RTFDH = ((ADTM - ASTDTM) / 60 / 60)$	adpc, adex
RTLDD	Relative time from start of the most recent infusion on study (h) done prior to the PK sample		For pre-dose samples, RTLDD will be calculated considering the most recent infusion done prior to the sample. For example, the RTLDD for the pre-dose in Cycle 2 will be computed from the start time of infusion in Cycle 1.	adpc

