RTLDD	Relative time from start of the most recent infusion on study (day) done prior to the PK sample		$RTLDD = RTLDDH / 24$	derived
NOMTLDD	Planned nominal time relative to start of most recent infusion (day)		$NOMTLDDH / 24$	adpc
NOMTLDDH	Planned nominal time relative to start of most recent infusion (h)		Derive from PCTPT when (PCTPT = 'PRE-DOSE'), NOMTLDDH = 0; when (PCTPT = 'DOSE'), NOMTLDDH = 0; when (PCTPT = "30M POST START OF INFUSION (SOI)"), NOMTLDDH = 0.5; when (PCTPT = "END OF INFUSION (EOI)"), NOMTLDDH = 1; when (PCTPT = "1 HOUR POST-EOI"), NOMTLDDH = 2; when (PCTPT = "3 HOURS POST-EOI"), NOMTLDDH = 4; when (PCTPT = "8 HOURS POST-EOI"), NOMTLDDH = 9; when (PCTPT = "24 HOURS POST-EOI"), NOMTLDDH = 25; when (PCTPT = "7 DAYS POST-EOI"), NOMTLDDH = 168; when (PCTPT = "14 DAYS POST-EOI"), NOMTLDDH = 336; when (PCTPT = "PRE-DOSE" and VISIT = CYCLE 2, NOMTLDDH = 504; when (PCTPT = "END OF STUDY"), NOMTLDDH = 10000;	adpc

CONFIDENTIAL

BMA117159

Column Header	Data Item	Codes	Derivation/Comments	Source data set
			otherwise NOMTLDH =.;	
CLOCK	Clock time sample was obtained	Clock time (24 h) '00:00'	TIMEPART (EVENT and DOSING LINE) Format TIME5.	all dataset
DATE	Date of event (MM/DD/YYYY)		DATEPART (EVENT and DOSING LINE) Format DATE9.	all dataset
ANALYTE	Analyte	1= ADC(antibody-drug conjugate) 2= TOTALMAB(total antibody including complex) 3= MMAF(cys-mcMMAF)	This value will be used on all lines except for dosing record line where missing "0" will be used. EXCLUDE MAB PARAMCD in (P1RES, P5RES, P7RES), assign ANALYTE =3, 1, 2 respectively	Derived from adpc
CONC	Plasma concentration (ng/mL) of GSK2857916 (antibody-drug conjugate), total antibody (including complex) and cys-mcMMAF		If AVALC=NA/NR/NQ/BQL/missing, set CONC= "0" Else CONC=AVAL When PARAMCD=P1RES, then CONC=AVAL/1000 [Convert cys-mcMMAF from pg/mL to ng/mL precision (3 significant figures). For example, 0.111 pg/mL= 0.000111 ng/mL]	adpc
DNCONC	Dose-normalized plasma concentration [(ng/mL)/(mg/kg)] of GSK2857916 (antibody-drug conjugate), total antibody (including complex) and cys-mcMMAF		DNCONC = CONC (ng/mL)/AVAL; where AVAL=adex.PARAMCD=ADOSE (mg/kg) For CONC = "0", set DNCONC = "0"	Derived from adpc, adex

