MDV	Missing dependent variable flag.	0 or 1	1 for CONC = "0" and dosing line. 0 otherwise	adpc
MDV2	Missing dependent variable flag 2	0 or 1	1 for CONC2= "0" and dosing line. 0 otherwise	adpc
EVID	Flag indicating whether it is dosing admin info or drug concentration data.	0 or 1	1 on dosing line Set to 0 for all other lines	adex, adpc
CYCLE	Cycle number	>0	1 = Cycle 1, 2 = Cycle 2, 3 = Cycle 3, 4 = Cycle 4, 5 = Cycle 5,... etc EOT=999 Derive from AVISIT Fill CYCLE on all rows Note: Pre-dose belongs to the same cycle as the post dose sample done on the same day.	adpc
OCC	Occasion		If adpc.PCTPT=PRE-DOSE and CYCLE >= 2, then OCC= CYCLE-1, else OCC=CYCLE Fill OCC on all rows Note: This is different from CYCLE variable. OCC considers pre-dose sample to be part of prior cycle.	derived
EXTSMP	Subjects with extensive sampling/data	0= Subjects which do not have	1 will be assigned to subjects which have at least 4 CONC values above BLQ for either ANALYTE=1 or ANALYTE=3 up in OCC=1 0 for remaining subjects	adpc

CONFIDENTIAL

BMA117159

Column Header	Data Item	Codes	Derivation/Comments	Source data set
		extensive CONC for ADC/MM AF 1= Subjects with extensive CONC for ADC/MMAF	Fill EXTSMP on all rows	
IDOSE	GSK2857916 initial cycle dose (mg/kg)	>0	IDOSE=adex.TRT01A; strip off units	adex
ADOSE	GSK2857916 actual cycle dose (mg/kg)	>0	ADOSE= AVAL; where AVAL=adex. PARAMCD=ADOSE	adex
CMT	Compartment	>0	1 = Dosing line 1= Central Compartment for antibody-drug conjugate when ANALYTE=1 3 = Central Compartment for total antibody (including complex) when ANALYTE=2 5 = Central Compartment for cys-mcMMAF when ANALYTE=3	
RACET	Subject race text	Use CRF/Stats coding	RACET=adrace.ARACE Fill in RACET in all rows for each subject	adrace
RACEN	Subject race numeric		4 - ASIAN - JAPANESE HERITAGE 3 - ASIAN - SOUTH EAST ASIAN HERITAGE 2 - BLACK OR AFRICAN AMERICAN 1 - WHITE - ARABIC/NORTH AFRICAN HERITAGE 0 - WHITE - WHITE/CAUCASIAN/EUROPEAN HERITAGE	adrace
ETHN	Subject ethnicity	Same coding as CRF/Stats	Fill in ETHN in all rows for each subject - If missing, ETHN = -99	adsl
AGE	Age (years)		• Use value as defined by Stats; • If not defined by Stats, AGE = date of first dose – date of birth • If date of birth is missing, AGE = -99	adsl
SEX	Gender	0 or 1	Male = 1 Female = 0	adsl

CONFIDENTIAL

BMA117159

Column Header	Data Item	Codes	Derivation/Comments	Source data set
			
 If sex is missing, SEX = -99 	

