 - Categorical covariates such as gender, race, disease status, immunogenicity status, and geographic region.
- Non-parametric bootstrapping may be performed to test model robustness. The model performance may be evaluated by performing predictive check.
- Individual *post hoc* estimated PK parameters will be summarized descriptively.

- Individual subject PK parameters and exposure measures for Cycle 1 will be estimated and documented for the purposes of any subsequent exposure-response (PK/PD) analyses.

Any analyses not described *a priori* but undertaken based on emerging data will be described in detail in the report.

Data handling considerations are summarized below:

- Drug concentration data which are below the lower limit of quantification, LLQ, (NQ or BLQ) are not reported as a numeric value. Such NQ observations will be either discarded or handled in a special way. When the frequency of NQ is small, the NQ values will be excluded, since discarding NQ values in this case introduces little bias [Beal, 2001]. In situations where there are a large percentage of NQ values, other strategies which may reduce estimation bias will be considered [Beal, 2001; Hing, 2001; Ahn, 2008]. The total number and percentage of NQ values will be calculated and the rationale for the method for handling these NQ values will be documented in the final report. In situations with large number of NQ values, the predictive performance of the model will be assessed to compare the agreement between observed versus predicted proportion of samples below the LLQ.
- Concentrations that are inconsistent pharmacokinetically with the drug concentration-time profile within an individual may be considered as outliers and subsequently excluded from the dataset or analysis. Visual inspection of individual and pooled data and weighted residuals during analysis may be used to identify such outliers. Any such exclusion will be reported and discussed in the analyses summary.
- Missing data will be handled in the following way:
 - Subjects who withdrew from the study and did not provide any PK samples and do not have adequate sampling and/or covariate information will be excluded from the analysis.
 - If dosing and/or sampling times are missing, the relevant concentrations may be excluded from the analysis dataset and summarized in an exclusion listing file. Alternatively, the nominal times of the respective doses and/or samples may be utilized.

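### Nominal time since last infusion is set to 0 h instead of 504 h for Cycle 3 and Cycle 5 pre-dose samples in the PopPK dataset

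*SAP*

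**What the plan says.** The PopPK dataset specification in SAP Section 16.9.1 includes a nominal-time column, NOMTLDDH, described as "Planned nominal time relative to start of most recent infusion (h" (that is, in hours). A companion column in days, NOMTLDD, is NOMTLDDH divided by 24.

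NOMTLDDH is derived from the planned time-point label through a list of conditions. For pre-dose and dosing records the list opens with "when (PCTPT = 'PRE-DOSE'), NOMTLDDH = 0; when (PCTPT = 'DOSE'), NOMTLDDH = 0". Further down, one visit-specific pre-dose condition appears: "and VISIT = CYCLE 2, NOMTLDDH = 504". No other cycle is named.

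Two other columns in the same table also place pre-dose samples:

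- The actual time since the last infusion: "For pre-dose samples, RTLDD will be calculated considering the most recent infusion done prior to the sample".
- The occasion: "If adpc.PCTPT=PRE-DOSE and CYCLE >= 2, then OCC= CYCLE-1, else OCC=CYCLE".

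On missing dosing or sampling times, Section 16.9.1 has an exclusion code, STM, used "If a PK sample was taken but the date and/or time of the sample is missing and cannot be derived". Section 16.9.2 lets the affected concentrations be excluded, and then adds: "Alternatively, the nominal times of the respective doses and/or samples may be utilized".

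**The concern.** The pre-dose rule does not match the column's own definition. A sample drawn just before the Cycle 3 or Cycle 5 dose comes at the end of the previous dosing interval, so the most recent infusion is the one given in the previous cycle. The specification recognises this for Cycle 2 and for no later cycle.

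If the column were used to stand in for a missing actual time, or as the time axis of an exploratory plot or summary, an end-of-interval trough would carry the label of a sample at the start of an infusion. Troughs carry much of the information on elimination and accumulation, so any records affected would be informative ones.

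**Working it through.** **Inputs**

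- Cycle length 21 days (titles of the time-and-events tables, Sections 16.2.2.1 and 16.2.3.1).
- Part 1 PK sampling (Section 16.2.2.1, footnotes 21 and 22). The last cycle with a pre-dose sample is Cycle 3: "C3D1 at pre-dose (within 30 minutes prior to SOI) and at the EOI (just before EOI".
- Part 2 MM PK sampling (Section 16.2.3.1, footnotes 24 and 25): pre-dose and end of infusion at Cycles 1, 2, 3 and 5, plus one sample at the final visit.
- Lymphoma subjects are excluded from this dataset (Section 16.9.1, general description, item 8), so their schedule does not count here.

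**Reproducing the plan's figure**

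Planned time from one infusion start to the next = 21 days x 24 h = 504 h. This is the value the plan gives for Cycle 2. Other entries in the list follow the same clock with a 1 h infusion: end of infusion 1; 1, 3, 8 and 24 h later 1 + 1 = 2, 1 + 3 = 4, 1 + 8 = 9 and 1 + 24 = 25. The column is therefore a real elapsed time at these points.

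**Applying the rule to each sampled cycle**

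| Pre-dose sample | Required by the definition | Rule, if later conditions override earlier ones | Rule, if the first match wins |
|---|---|---|---|
| Cycle 1 | 0 h by convention (no earlier infusion) | 0 h | 0 h |
| Cycle 2 | 504 h | 504 h | 0 h |
| Cycle 3 | 504 h | 0 h | 0 h |
| Cycle 5 | 504 h | 0 h | 0 h |

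The shortfall at Cycles 3 and 5 is 504 - 0 = 504 h, or 504 / 24 = 21 days in NOMTLDD. Neither coding convention gives the required column. If conditions are tested in the written order and stop at the first match, the Cycle 2 exception is never reached either.

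**Scheduled PK times affected per subject**

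- Part 2 MM: 4 cycles x 2 samples + 1 final visit = 9. Wrong: Cycle 3 and Cycle 5 pre-dose, 2 of 9 (22%).
- Part 1: Cycle 1 Days 1 to 2, 7 samples; Day 8, 1; Day 15, 1; Cycle 2, 2; Cycle 3, 2; final visit, 1; total 14. Wrong: Cycle 3 pre-dose, 1 of 14 (7%).
- Among pre-dose samples after Cycle 1: 2 of 3 in Part 2 MM and 1 of 2 in Part 1.

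**Consistency with the rest of the plan**

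The actual-time rule and OCC both attach every pre-dose sample from Cycle 2 on to the preceding infusion or cycle. Section 9.3.1.3 does the same: it takes trough as the concentration just before the next cycle's dose and analyses it for Cycles 1, 2 and 4, which are the Cycle 2, 3 and 5 pre-dose samples.

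**The case against.** The strongest reply concerns weight. The dataset carries actual times and is sorted on them, and Section 16.9.2 never names NOMTLDD or NOMTLDDH. The substitution of nominal times is optional, is an alternative to exclusion, and does not say which nominal column would be used. Pre-dose samples are planned within 30 minutes before the infusion, so a missing clock time on a known dosing day could often be recovered from that day's infusion record. Read against the same visit's infusion, 0 h is roughly the right calendar position; the 504 h displacement arises only when 0 is counted from the previous infusion. The column also holds a placeholder, 10000 h for end of study, and the CYCLE column groups a pre-dose sample with the dose that follows it. Finally, Section 16.9.1 commits to documenting departures of the final dataset from the specification.

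Most of this stands as a limit on impact, and none of it removes the mismatch. The column's definition fixes the anchor as the most recent infusion, which for a pre-dose sample is the previous one. The 504 h entry for Cycle 2 rules out reading 0 as a mere pre-dose label, since Cycle 2 and Cycle 3 troughs are the same kind of sample. The CYCLE note says which visit a sample belongs to and does not define time since the last infusion. The placeholder covers a visit with no fixed planned interval, whereas pre-dose samples have one.

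**Conclusion.** The concern holds, at minor severity. As written, the rule puts every Cycle 3 and Cycle 5 pre-dose record 504 h (21 days) below the value its definition requires, and Cycle 2 is right only under one way of coding the conditions. The fault is an incomplete derivation rule; the 504 h figure itself is correct.

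The shares of 2 of 9 and 1 of 14 are per-schedule maxima, because subjects who stop before Cycle 3 or Cycle 5 contribute fewer such samples. A model fit on actual times is unaffected. The number of missing actual times is not stated, so the effect on PK estimates cannot be quantified and may be zero. It would arise only if nominal times were substituted using this column, counted from the previous infusion, or if exploratory displays used it.

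**What to change.** Replace the two pre-dose conditions for NOMTLDDH with:

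- PRE-DOSE and CYCLE = 1: NOMTLDDH = 0
- PRE-DOSE and CYCLE >= 2: NOMTLDDH = 504

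Delete the unrestricted pre-dose condition, so that the result no longer depends on the order in which conditions are evaluated. NOMTLDD then corrects itself to 21 days. The cost is one line of the dataset specification, with no new data and no change to the model.

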CRCL	Creatinine Clearance (mL/min/1.73 m ²)		
To be computed with same equation as provided for BCRCL
 
CRCL is propagated forward from the most recent measurement for all observations up to the next CRCL measurement (LOCF). Please capture the values corresponding to the PK time points.
	adlb		
BALT	Baseline ALT (IU/L)		
BALT = AVAL; AVAL=adlab. PARAMCD =LB1227 and ABLFL=Y Use baseline covariate rules
	adlb		
ALT	ALT (IU/L)		
ALT = AVAL; AVAL=adlab. PARAMCD =LB1227 and ABLFL=Y ALT is propagated forward from the most recent measurement for all observations up to the next ALT measurement (LOCF). Please capture the values corresponding to the PK time points.
	adlb		
BAST	Baseline AST (IU/L)		
BAST = AVAL; AVAL=adlab. PARAMCD =LB1273 and ABLFL=Y Use baseline covariate rules
	adlb		
AST	AST (IU/L)		
AST = AVAL; AVAL=adlab. PARAMCD =LB1273 and ABLFL=Y AST is propagated forward from the most recent measurement for all observations up to the next AST measurement (LOCF). Please capture the values corresponding to the PK time points.
	adlb		
BALB	Baseline Albumin (g/L)		
BALB = AVAL; AVAL=adlab. PARAMCD =LB1216 and ABLFL=Y Use baseline covariate rules
	adlb		
ALB	Albumin (g/L)		
ALB = AVAL; AVAL=adlab. PARAMCD =LB1216 and ABLFL=Y ALB is propagated forward from the most recent measurement for all observations up to the next ALB measurement (LOCF). Please capture the values corresponding to the PK time points.
	adlb		
BTBIL	Baseline Total Bilirubin (mg/dL)		
BTBIL = AVAL; AVAL=adlab. PARAMCD =LB1282 and ABLFL=Y
	adlb		

CONFIDENTIAL

BMA117159

Column Header	Data Item	Codes	Derivation/Comments	Source data set
			Use baseline covariate rules	
TBIL	Total Bilirubin (mg/dL)		TBIL = AVAL; AVAL=adlab. PARAMCD =LB1282 and ABLFL=Y TBIL is propagated forward from the most recent measurement for all observations up to the next TBIL measurement (LOCF). Please capture the values corresponding to the PK time points.	adlb
BCRP	Baseline C Reactive Protein (mg/L)		Use baseline covariate rules	adlb
CRP	C Reactive Protein (mg/L)		CRP is propagated forward from the most recent measurement for all observations up to the next CRP measurement (LOCF). Please capture the values corresponding to the PK time points.	
BIGG	Baseline serum IgG (g/L)		BIGG = AVAL; AVAL=adlab. PARAMCD =LB1566 and ABLFL=Y Use baseline covariate rules	adlb

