IGG	Serum IgG (g/L)		IGG = AVAL; AVAL=adlab PARAMCD =LB1566 Missing values use -99. IGG is propagated forward from the most recent measurement for all observations up to the next IGG measurement (LOCF). Please capture the values corresponding to the PK time points.	adlb
MAXPRED	Maximum reduction in M-protein or FLC		Obtain AVAL for PARAMCD=MAXPRED. When AVAL is missing, MAXPRED = -999	adrs
RESPRATIO	Transform MAXRED to a ratio to baseline		RESPRATIO = $\max((100+\text{MAXPRED})/100, 0.001)$ 
 • When MAXRED is missing, MAXPRED = -999 and RESPRATIO= -99 • When MAXPRED is less than -100 e.g. -100.15, RESPRATIO = negative (It is negative but greater than -8.99), then update RESPRATIO = 0.001 • When MAXPRED is equal to -100, RESPRATIO = 0, then update RESPRATIO = 0.001 	adrs
COUNTRY	Country code		Fill in COUNTRY in all rows for each subject	adsl
CNC	NONMEM Country code	1 = Canada, 2 = UK	Fill in CNC in all rows for each subject	adsl

CONFIDENTIAL

BMA117159

Column Header	Data Item	Codes	Derivation/Comments	Source data set																												
		3 = US																														
IMMU	Immunogenicity Outcome by Collection Time	0 = negative 1 = positive	
  
 	PARAMCD	IMMU	
 
 	PARAMCD = AGBABDS	PARAMCD = AGBABDC		
   
 AVAL C	NEGATIVE	MISSING	0	
 
 AVAL C	POSITIVE	POSITIVE	1	
 
 AVAL C	POSITIVE	NEGATIVE	0	
 
 AVAL C	POSITIVE	MISSING	-99	
 
 AVAL C	MISSING	ANY	-99	
  
 
IMMU may not have been assayed at all PK visits. For visits between IMMU visits, imputation rules are as follows:
 
(1) When there is no change in IMMU between IMMU visits, all PK visits in between will be imputed with
		PARAMCD		IMMU		PARAMCD = AGBABDS	PARAMCD = AGBABDC		AVAL C	NEGATIVE	MISSING	0	AVAL C	POSITIVE	POSITIVE	1	AVAL C	POSITIVE	NEGATIVE	0	AVAL C	POSITIVE	MISSING	-99	AVAL C	MISSING	ANY	-99	adis
	PARAMCD		IMMU																													
	PARAMCD = AGBABDS	PARAMCD = AGBABDC																														
AVAL C	NEGATIVE	MISSING	0																													
AVAL C	POSITIVE	POSITIVE	1																													
AVAL C	POSITIVE	NEGATIVE	0																													

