16.9.2. Population Pharmacokinetic (PopPK) Methodology

The primary goal of this analysis is to characterize the population pharmacokinetics of GSK2857916 and associated analytes after intravenous administration of GSK2857916 in subjects with multiple myeloma. This analysis will be performed by CPMS and reported separately.

A summary of the planned population pharmacokinetic analyses is outlined below:

- Exploratory data analyses will be performed to understand the content of the analysis dataset with respect to the anticipated models, to search for extreme values and/or potential outliers, to examine the correlation between covariates, and to assess possible trends in the data.
- Drug concentration-time data will be subjected to nonlinear mixed effects modelling using appropriate validated software to develop a population PK model.
- Based on the preliminary analysis, log-transformed drug concentration data for GSK2857916 ADC will be subjected to analysis using a two-compartment IV infusion model parameterized using either clearances and distribution volumes, micro-constants or macro-constants (A, B, ALPHA and BETA), depending on parameters to be estimated. A similar approach may be used on the data from the three analytes (ADC, total antibody, and cys-mcMMAF) together.
- Inter-individual or between-subject variability (IIV or BSV) will be initially modeled using an exponential random effects model. Random effects for clearances and volumes or A and B and BETA will be incorporated, depending on model parameterization used. If the goodness-of-fit plots reveal potential biases in the random effects model, alternative random effects models may be considered.
- An additive error model on a log-transformed data scale reflecting an exponential error residual variability model will initially be used to describe the residual variability. If the goodness-of-fit plots reveal potential biases in the residual variability model, other residual error models will be considered as appropriate.
- Covariate analysis will be performed to explore measurable sources of PK variability. Different approaches may be evaluated for covariate model building including a step-wise process consisting of a forward and a backward selection procedure and/or a full-model approach. Some of the prospectively identified covariates are listed below:
 - Continuous covariates such as age, albumin, measures of body size (e.g., body weight, body surface area, body mass index, lean body mass);

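### The PopPK specification restricts the on-treatment ALT, AST, albumin and bilirubin columns to baseline records, contradicting the carry-forward instruction in the same rows

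*SAP*

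**What the plan says.** SAP Section 16.9.1 gives many laboratory covariates two columns: one fixed at baseline and one meant to follow the subject over time.

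- The baseline ALT column reads "BALT = AVAL; AVAL=adlab. PARAMCD =LB1227 and ABLFL=Y Use baseline covariate rules".
- The on-treatment ALT column reads "PARAMCD =LB1227 and ABLFL=Y ALT is propagated forward from the most recent measurement". The row goes on to say that a value holds until the next ALT result and that the values should correspond to the PK time points.
- AST, albumin and total bilirubin have the same construction: "PARAMCD =LB1273 and ABLFL=Y AST is propagated forward from the most recent measurement", "PARAMCD =LB1216 and ABLFL=Y ALB is propagated forward from the most recent measurement" and "PARAMCD =LB1282 and ABLFL=Y TBIL is propagated forward from the most recent measurement".
- Serum IgG is built differently. Its baseline column BIGG carries the flag, but its on-treatment column does not: "IGG = AVAL; AVAL=adlab PARAMCD =LB1566 Missing values use -99". The same carry-forward instruction follows.

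Section 5.2 defines baseline as the last non-missing value before dosing, so there is one baseline value per subject and test. Section 16.9.2 names albumin among the covariates to be explored: "Continuous covariates such as age, albumin, measures of body size".

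**The concern.** The four rows give two instructions that exclude each other. One keeps only the baseline record. The other presupposes a series of records, each replacing the one before. A programmer who applies the filter gets a column that never changes. A programmer who applies the carry-forward text must ignore part of the derivation. The specification does not say which instruction governs, so two people working from it could build different datasets.

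At stake is whether the PopPK dataset can be used to look at on-treatment change in liver tests and albumin. If the filter is followed, it cannot. The error is also not obvious when looking at one column alone: the columns are populated, the values are plausible, and the labels do not say baseline.

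**Working it through.** No figure in the plan needs reproducing, so the check is a comparison of rows in Section 16.9.1.

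| Test | Filter on baseline column | Filter on on-treatment column | Carry-forward ordered for on-treatment column |
|---|---|---|---|
| ALT (LB1227) | ABLFL=Y | ABLFL=Y | yes |
| AST (LB1273) | ABLFL=Y | ABLFL=Y | yes |
| Albumin (LB1216) | ABLFL=Y | ABLFL=Y | yes |
| Total bilirubin (LB1282) | ABLFL=Y | ABLFL=Y | yes |
| IgG (LB1566) | ABLFL=Y | none | yes |
| Soluble BCMA | ABLFL=Y | none | yes |
| CRP | general baseline rules | none | yes |
| Weight | general baseline rules | none | yes |
| Creatinine clearance (creatinine LB1404) | ABLFL=Y | not stated; refers to the BCRCL equation | yes |

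**Step 1: meaning of the flag.** Throughout the table ABLFL=Y picks out the baseline record (BSBCMA, BCRCL, BALT, BAST, BALB, BTBIL, BIGG). With the Section 5.2 definition, that is one pre-dose record per subject and test.

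**Step 2: what the filter leaves.** After filtering there is one record and no later one. Carrying one record forward gives a constant. For any subject with a flagged baseline, ALT = BALT, AST = BAST, ALB = BALB and TBIL = BTBIL on every row to which the baseline is carried.

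**Step 3: subjects without a flagged baseline.** The general rules at the start of Section 16.9.1 let the baseline column fall back to the nearest pre-dose value, then screening, then -99. The four on-treatment rows state no fallback. The two columns need not agree for such subjects.

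**Step 4: what could have been used.** The dataset takes values at PK time points and contains myeloma subjects only. Comparing the PK and clinical chemistry lines of the every-3-weeks schedules, the PK days after Cycle 1 Day 1 that also have scheduled chemistry are:

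- Part 1 (Section 16.2.2.1): C1D2, C1D8, C1D15, C2D1, C3D1 and the end-of-treatment visit, 6 days.
- Part 2 myeloma (Section 16.2.3.1): C2D1, C3D1, C5D1 and the end-of-treatment visit, 4 days.

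This assumes that all four tests are in the clinical chemistry panel; the SAP refers to the protocol for the list. A subject who stops early contributes fewer days.

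**Step 5: intent.** The IgG, soluble BCMA, CRP and weight rows carry values forward with no baseline filter. The four rows depart from the table's own pattern, and each sits beside a baseline column that already holds the constant. The likely explanation is that the condition was copied from the baseline row. That is an inference, though a strong one.

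**Step 6: creatinine clearance.** CRCL is to use the BCRCL equation, and BCRCL takes its creatinine from ABLFL=Y records. The text does not say whether that restriction comes with the equation, so CRCL may share the problem.

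**The case against.** The best reply is that the intent is readable. The carry-forward text is explicit, a second constant column would be pointless, and the table is written in working shorthand. A careful programmer would probably drop the filter. The exploratory step in Section 16.9.2 includes looking at correlation between covariates, where two identical columns would stand out. Section 16.9.1 also promises that departures from the specification will be documented. All of this makes an unnoticed error less likely. It does not correct the text: a dataset built exactly as specified would contain no departure to document. The later end-of-study amendment changes only the list of displays and leaves these rows as they are.

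A reader might infer more than the documents support:

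- **That the report would claim time-varying covariates had been assessed.** Sections 10 and 16.9.2 promise no such test. Section 16.9.2 names albumin without saying whether baseline or on-treatment values will be modelled.
- **That albumin could not be assessed at all.** BALB is correctly specified, so a baseline albumin effect can be examined.
- **That exposure-response results would be materially changed.** Section 16.9.2 hands Cycle 1 parameters and exposure measures to the PK/PD work, and the Cmax, Ctau and AUC inputs in Section 16.10.1 are first-dose quantities. The time-averaged AUCs cover longer periods, but they use individual clearance values and no time-varying clearance is described.
- **That baseline and on-treatment models would always fit identically.** The columns must match only for subjects with a flagged baseline.

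**Conclusion.** The point holds as a contradiction within four rows of the dataset specification. Under the literal filter, all post-baseline information on ALT, AST, albumin and total bilirubin is lost from the on-treatment columns for every subject with a flagged baseline: up to 6 scheduled update days in Part 1 and up to 4 in Part 2 myeloma. The PopPK dataset then cannot be used to explore on-treatment change in these tests.

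The reach is limited to the PopPK covariate analysis, which is reported separately. The safety and response analyses do not use these columns. The conclusion rests on ABLFL=Y marking one pre-dose record per subject and test, which follows from Section 5.2 and from the flag's use elsewhere in the table. It is worth correcting because the rule as written produces the wrong dataset and the correction costs almost nothing.

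**What to change.** In Section 16.9.1, delete the ABLFL=Y condition from the ALT, AST, ALB and TBIL rows and keep it on BALT, BAST, BALB and BTBIL, matching the BIGG and IGG pair. In the CRCL row, state that creatinine is taken at each visit and carried forward, rather than from the ABLFL=Y creatinine specified for BCRCL.

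The cost is five row edits (four deletions and one clarifying sentence). No new data are needed. If the dataset has already been programmed, check whether each on-treatment column differs from its baseline partner on any post-baseline row, and rebuild the columns that do not.
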